6.4.6. Platinum Chemotherapy Associated Toxicities Leading to Discontinuation of Study Treatment

The subject must discontinue platinum chemotherapy if:

- the subject experiences a Grade 3 or 4 unacceptable AE that does not resolve to Grade ≤ 1 within 7 days with medical management. Unacceptable AEs are described in [Appendix 2 Table 8](#).

- the subject experiences any other intercurrent illness that prevents further administration of treatment, the subject must discontinue study treatment.

Appendix 2 Table 8: Unacceptable Adverse Events Leading to Discontinuation of Platinum Chemotherapy

Grade 4 Hematologic toxicities	Grade 3 Non- hematologic toxicities
Complete Blood Count: 
 leukopenia thrombocytopenia neutropenia anemia 	Nephrotoxicity: 
 elevation in BUN and creatinine elevation in serum uric acid decrease in CrCl
Serum electrolyte disturbances: 
 hypomagnesemia hypocalcemia hyponatremia hypokalemia hypophosphatemia 	Ototoxicity: 
 tinnitus bilateral hearing loss dizziness
	Gastrointestinal: 
 nausea vomiting

For more information regarding the following sections, please refer to the main body of the protocol.	Page #
Section 7 Treatment Compliance	Page 101
Section 8 Concomitant Therapy	Page 102
Section 9 Study Evaluations	Page 105
Section 9.1 Study Procedures	Page 105
Section 9.2 Efficacy Evaluations	Page 108
Section 9.3 Pharmacokinetics and Immunogenicity	Page 110
Section 9.4 Pharmacodynamic Evaluations	Page 111
Section 9.5 Predictive and Exploratory Biomarkers	Page 111
Section 9.6 Safety Evaluations	Page 113
Section 9.7 Sample Collection and Handling	Page 117
Section 10 Subject Completion/Discontinuation of Study Treatment/Withdrawal From the Study	Page 117

Section 11 Statistical Methods	Page 118
Section 12 Adverse Event Reporting	Page 123
Section 13 Product Quality Complaint Handling	Page 130
Section 14 Study Drug Information	Page 130
Section 15 Study-Specific Materials	Page 133
Section 16 Ethical Aspects	Page 133
Section 17 Administration Requirements	Page 138

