Appendix 2 Table 7 : Dose Modifications for Cisplatin and Carboplatin

Category	Cisplatin		Carboplatin	
Starting dose	50 mg/m ²	60 mg/m ²	AUC 4 mg/mL/min (maximum dose 600 mg)	AUC 5 mg/mL/min (maximum dose 750 mg)
1st dose modification	Stop cisplatin but continue erdafitinib+ cetrelimab	50 mg/m ²	Stop carboplatin but continue erdafitinib+ cetrelimab	AUC 4.5 mg/mL/min (maximum dose 675 mg)
2nd dose modification	N/A	Stop cisplatin but continue erdafitinib+ cetrelimab	N/A	Stop carboplatin but continue erdafitinib+ cetrelimab

Creatinine clearance (CrCl)

CrCl will be based on the original weight-based Cockcroft and Gault formula ([Attachment 8](#)). The subject's CrCl at Screening must be ≥ 30 mL/min to receive carboplatin and ≥ 60 mL/min to receive cisplatin prior to each cycle of platinum chemotherapy. Cisplatin may be delayed for up to 21 days (1 cycle) to allow the subject time to recover from the toxicity. If a subject's CrCl value has not returned to ≥ 30 mL/min within 42 days (2 cycles) after the previous dose, cisplatin must be discontinued.

In general, study drug(s) should be held for AEs \geq Grade 3 that are not attributable to erdafitinib, cetrelimab, platinum chemotherapy, or the disease under study. If the event resolves to Grade 1 or baseline within 4 weeks, platinum chemotherapy and erdafitinib may be reintroduced at one dose level lower. If the same toxicity does not recur or worsen within 4 weeks after re-starting therapy, then cetrelimab may be reintroduced at the same dose. Following re-introduction of study drugs, if the same AE recurs at \geq Grade 3 or there is a second incidence of a \geq Grade 3 event that is not attributable to erdafitinib, cetrelimab, platinum chemotherapy, or the disease under study, study drugs should be permanently discontinued.

For toxicity associated with platinum chemotherapy, the AE must resolve to Grade ≤ 1 or baseline prior to starting subsequent cycle. For individual subjects requiring a dose modification, treatment

for each new cycle may be delayed if the scheduled off-drug periods are not adequate to allow for recovery to Grade ≤ 1 or the baseline status of the subject.

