6.4.5. Guidance for Specific Platinum Chemotherapy Toxicities

Cisplatin

The toxicity profile for cisplatin is described in the full prescribing information and labeling in the respective current US prescribing information, EU SmPC, or equivalent document for the specific region/country.

For subjects in DL2C, DL2C1 and DL2C2, cisplatin may produce cumulative nephrotoxicity which is potentiated by aminoglycoside antibiotics. Serum creatinine, blood urea nitrogen (BUN), creatinine clearance, magnesium, sodium, potassium, and calcium levels should be measured prior to initiating therapy and prior to each dose of cisplatin. Adequate renal function must be documented prior to receiving the next dose of cisplatin.

Audiometry will be performed for cis-ineligible ONLY if hearing loss is the single reason for cis-ineligibility. Audiometry will be performed as clinically indicated as ototoxicity is cumulative. Hearing loss during the study should be reported as an AE and graded according to CTCAE version 5.0.

Carboplatin

The toxicity profile for carboplatin is described in the full prescribing information and labeling in the respective current US prescribing information, EU SmPC, or equivalent document for the specific region/country.

For subjects in DL2D and DL2D1, bone marrow suppression (leukopenia, neutropenia, and thrombocytopenia) is dose-dependent and is also a DLT. Peripheral blood counts should be monitored frequently and, when appropriate, until recovery is achieved. Carboplatin can induce emesis, which can be more severe in patients previously receiving emetogenic therapy.

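### Protocol Appendix 2 sets two stop limits for a Grade 3–4 CrCl decrease on cisplatin, 7 days (6.4.6) and 42 days (6.4.4), and does not say which governs

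*Protocol*

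**What the plan says.** All places are in Protocol Appendix 2 unless stated otherwise.

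- **6.4.6 and Table 8.** Platinum must be discontinued when a Grade 3 or 4 unacceptable adverse event does not resolve to Grade 1 or lower "within 7 days with medical management". Under nephrotoxicity, Table 8 lists "decrease in CrCl".
- **6.4.4, Creatinine clearance paragraph (below Table 7).** "Cisplatin may be delayed for up to 21 days (1 cycle) to allow the subject time to recover from the toxicity". If CrCl has not returned to at least 30 mL/min "within 42 days (2 cycles) after the previous dose, cisplatin must be discontinued".
- **Conditions for re-dosing.** The CrCl paragraph asks for at least "60 mL/min to receive cisplatin prior to each cycle of platinum chemotherapy". 6.4.4 also wants a platinum toxicity resolved to Grade 1 or lower "or baseline prior to starting subsequent cycle". 6.4.5 adds: "Adequate renal function must be documented prior to receiving the next dose of cisplatin".
- **Dose steps.** Table 6 gives one dose-modification step (DM -1) for other Grade 3 or 4 non-hematological toxicity. In Table 7 the first modification is a stop for a 50 mg/m² starter and a reduction to 50 mg/m² for a 60 mg/m² starter. 6.4.4 describes Tables 5 and 6 as guidance.
- **Tie-break.** 6.4.4, like 6.5 of the main protocol, says to follow the most conservative adjustment when recommendations conflict, but words this for a subject with several toxicities.

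**The concern.** One toxicity has two mandatory stop rules with different deadlines and different recovery targets: Grade 1 or lower in 6.4.6, at least 30 mL/min in 6.4.4. Neither section refers to the other. The tie-break does not literally apply, because this is one toxicity under two rules.

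It is also hard to read 6.4.4 as meant only for milder events. It has no grade limit. Cisplatin subjects must enter with CrCl of at least 60 mL/min, so a value below 30 mL/min is less than half the entry minimum.

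At stake is consistency. One site may end cisplatin permanently at 7 days. Another may rely on the CrCl-specific paragraph, wait for recovery and resume at the lower dose.

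**Working it through.** **Inputs.** Cycle length 21 days (synopsis). 7-day limit (6.4.6). 21-day delay and 42-day limit (6.4.4). CrCl test days (Appendix 2 Table 1). Planned numbers (main protocol 11.1.1). Maximum of 4 cisplatin cycles (6.4.1).

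**The plan's own figure.** 21-day cycle + 21-day delay = 42 days = 2 cycles. 6.4.4 is therefore consistent with itself on timing.

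**Gap between the limits.** Count days from the previous dose, on nominal visit days and with no earlier delay. 6.4.6 does not say when its 7 days begin; assume they begin at the scheduled test. For a test t days after the dose, the 6.4.6 limit is t + 7, the 6.4.4 limit is 42, and the gap is 42 − (t + 7).

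| Test | t | 6.4.6 limit | 6.4.4 limit | Gap |
|---|---|---|---|---|
| Day 8 | 7 | 14 | 42 | 28 days |
| Day 15 | 14 | 21 | 42 | 21 days |
| Next Day 1 | 21 | 28 | 42 | 14 days |

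The limits coincide only at t = 42 − 7 = 35 days. A clock that starts later than the test shortens each gap by the same number of days.

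**Scheduled tests.** Seven CrCl tests follow the first cisplatin dose: C1D8, C1D15, C2D1, C2D8, C2D15, C3D1 and C4D1. The gap is 28 days at two of them, 21 days at two and 14 days at three. After the fourth dose the question is moot.

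**Who is exposed.** Under Tables 6 and 7, a 50 mg/m² starter with such an event is stopped at the first modification anyway. A 60 mg/m² starter goes to 50 mg/m². Planned cisplatin subjects, if the starting dose is safe: 3 + 6 + about 10 = about 19. Those starting at 60 mg/m² number 6 if the MTD is 50 mg/m², or 6 + 10 = about 16 if it is 60 mg/m².

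**Largest effect on one subject.** Take a 60 mg/m² starter with an event at C1D8 that is unresolved at 7 days but recovers in time. Under 6.4.6 the subject receives one dose, 60 mg/m². Under 6.4.4 the subject may receive up to four: 60 + 3 × 50 = 210 mg/m².

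**The case against.** The strongest reply is that both rules can be obeyed. The delay in 6.4.4 is permissive and the stop in 6.4.6 is mandatory. Two mandatory stop conditions are both met by stopping at the earlier one, and the protocol's most-conservative principle points the same way. On that reading the site that waits has breached 6.4.6.

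This stands in part: compliance with both clauses is possible, so a reader who infers that no site could comply with both goes too far. But the reading cancels the explicit 21-day delay and 42-day limit for Grade 3–4 events found at any of the seven scheduled tests. Nothing in the text says that was intended.

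Other stronger inferences are also unsupported:

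- **That an unrecovered subject would be re-dosed.** The 60 mL/min threshold, the adverse-event resolution rule and the documented renal function check all stand in the way.
- **That DLT counts are affected.** Five of the seven tests (C1D8 to C2D15) fall inside the 6-week DLT period, and DLT status depends on the event, not on whether cisplatin later stops or resumes.
- **That the sentence letting treatment "for each new cycle may be delayed if the scheduled off-drug periods are not adequate to allow for recovery" is a further conflict.** It is a general allowance for dose-modified subjects on either platinum drug and sets no CrCl deadline. The point does not rest on it.
- **That the laboratory panel is part of the same defect.** Section 9.6.2 lists neither BUN nor uric acid. But 6.4.5 itself orders BUN before each cisplatin dose, and a Table 8 item need not have a scheduled test. This is minor housekeeping.

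**Conclusion.** The point holds. Appendix 2 gives a Grade 3–4 CrCl decrease on cisplatin two deadlines and two recovery targets, with no statement of precedence. The likely effect is inconsistent permanent stopping versus resumption at 50 mg/m², mainly among subjects starting at 60 mg/m². The 6 to about 16 such subjects are a denominator; the protocol gives no basis for estimating how many would have the event.

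The size rests on three assumptions: the 7-day clock starts at the scheduled test, visits fall on nominal days, and investigators follow Table 6, which is guidance only (hence mainly, not solely, 60 mg/m²). The protocol prints no CTCAE cut-offs for CrCl, but the conflict does not depend on them because 6.4.4 is not limited by grade. No sample size, interval or error rate changes. The weight is minor to modest.

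**What to change.** Add one sentence to the CrCl paragraph of Appendix 2, 6.4.4: section 6.4.6 takes precedence, and the 21-day delay and 42-day limit apply only to CrCl decreases that do not meet the 6.4.6 criterion. This agrees with the protocol's most-conservative principle. The same edit could say when the 7 days begin. If BUN and uric acid are tidied at all, do so as housekeeping in the same amendment.

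The cost is one sentence, with no new visit, sample or analysis.

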APPENDIX 3: PHASE 2 ERDAFITINIB +/- CETRELIMAB COHORT

1. INTRODUCTION.....	233
2. OBJECTIVES, ENDPOINTS, AND HYPOTHESIS.....	233
2.1. Objectives and Endpoints for Phase 2 (Dose Expansion)	233
2.2. Hypothesis	233
3. STUDY DESIGN AND RATIONALE	234
3.1. Overview of Study Design.....	234
3.1.1. Phase 1b.....	234
3.1.2. Phase 2: Erdafitinib +/- Cetrelimab Cohort.....	234
3.2. Study Design and Starting Dose Rationale.....	234
3.3. Dose-Limiting Toxicity Evaluation and Determination of RP2D.....	234
3.4. Study Evaluation Team.....	234
4. SUBJECT POPULATION.....	234
4.1. Inclusion Criteria	235
4.2. Exclusion Criteria	240
5. TREATMENT ALLOCATION AND BLINDING.....	244
6. DOSAGE AND ADMINISTRATION	244
6.1. Dose Combination for Erdafitinib +/- Cetrelimab Arms.....	244

Appendix 3 Table 1: Time and Events Schedule – Phase 2 Erdafitinib +/- Cetrelimab Cohort (Up to and Including Amendment 4)

Assessments/ Procedure	Notes	Molecular Eligibility Screening Period	Full-Study Screening Period	Treatment Cycle 1 ^g		Treatment Cycle 2 ^{g, 3}		All Other Cycles ^g		End-of-Treatment ^{a, g}	Follow-up Period ^{a, g}
		≥28 days prior to C1D1	Within 28 days prior to C1D1	Day 1	Day 15 (±2)	Day 1 (±2)	Day 15 (±2)	Day 1 (±2)	Day 15 (±2) ^f	Within 30 Days (+7) of last dose	Every 12 weeks
Screening Assessments											
Informed Consent (molecular and full-study)	Molecular Eligibility ICF to allow for assessment of FGFR status from archived tumor tissue, blood or local report. Full-Study ICF within 35 days prior to C1D1 to be used for subjects who meet molecular eligibility criteria. Must be signed before any study-related activity ^b		X	X							
Eligibility Criteria	Details provided in Sections 4.1 and 4.2 of Appendix 3.			X							
Demography, and Medical History	Histology and cytology, staging, prior therapy, and response.			X							
Molecular Eligibility Determination											
Local FGFR results (where applicable) ⁱ	Subjects may enroll based on local test results.	X									

Assessments/ Procedure	Notes	Molecular Eligibility Screening Period	Full-Study Screening Period	Treatment Cycle 1 ^g		Treatment Cycle 2 ^{g, 3}		All Other Cycles ^g		End-of-Treatment ^{a, g}	Follow-up Period ^{a, g}
		≥28 days prior to C1D1	Within 28 days prior to C1D1	Day 1	Day 15 (±2)	Day 1 (±2)	Day 15 (±2)	Day 1 (±2)	Day 15 (±2) ^f	Within 30 Days (+7) of last dose	Every 12 weeks
	
 Subjects with local FGFR tissue or blood must submit test report to the sponsor for central verification. Subjects enrolling based on local testing must submit archival or fresh tumor tissue and a blood sample for retrospective confirmation of FGFR status as soon as possible after enrollment. The results of retrospective central confirmation do not affect the subject's eligibility for the study. 										
Central Testing from Tissue and Blood ⁱ	Archival or fresh biopsy tumor tissue and a blood sample should be submitted	X									

Appendix 3: Phase 2 Erdafitinib +/- Cetrelimab Cohort

CONFIDENTIAL – FOIA Exemptions Apply in U.S.

Approved, Date: 11 July 2022

224

Assessments/ Procedure	Notes	Molecular Eligibility Screening Period	Full-Study Screening Period	Treatment Cycle 1 ^g		Treatment Cycle 2 ^{g, 3}		All Other Cycles ^g		End-of-Treatment ^{a, g}	Follow-up Period ^{a, g}
		≥28 days prior to C1D1	Within 28 days prior to C1D1	Day 1	Day 15 (±2)	Day 1 (±2)	Day 15 (±2)	Day 1 (±2)	Day 15 (±2) ^f	Within 30 Days (+7) of last dose	Every 12 weeks
	for molecular eligibility screening. If fresh biopsy, subject must sign the Full-Study ICF.										
Study Drug Administration^c											
Erdafitinib	See Sections 6.1 and 6.2.			Oral once daily							
Cetrelimab infusion (Arm B only)	See Sections 6.1 and 6.3.			X ^c	X	X	X	X	X		
Safety Assessments											
Vital Signs (temperature, blood pressure, pulse/heart rate, respiratory rate)	Monitor every 15-20 min during the 1 st infusion; for monitoring during subsequent infusions. See Section 6.3.		X	X ^j	X	X	X	X	X	X	X ^d
Physical Examination (PE)	Complete PE including height and weight at Screening. Thereafter disease-directed PE. See Section 9.6.9.		X	X	X	X	X	X	X	X	X ^d
ECOG PS	See Attachment 3.		X	X	X	X	X	X	X	X	
12-lead ECG ^k	Results obtained within 60 days of C1D1 can be counted as screening assessment. Record post-dose ECGs. See		X		C2 only		C4 only		X		

Assessments/ Procedure	Notes	Molecular Eligibility Screening Period	Full-Study Screening Period	Treatment Cycle 1 ^g		Treatment Cycle 2 ^{g, 3}		All Other Cycles ^g		End-of-Treatment ^{a, g}	Follow-up Period ^{a, g}
		≥28 days prior to C1D1	Within 28 days prior to C1D1	Day 1	Day 15 (±2)	Day 1 (±2)	Day 15 (±2)	Day 1 (±2)	Day 15 (±2) ^f	Within 30 Days (+7) of last dose	Every 12 weeks
	Section 9.6.5 for exact timing. May be performed more often as clinically indicated.										
Echocardiogram or MUGA	Results obtained within 6 months of C1D1 can be counted as screening assessment provided the subject has not experienced any cardiac event in the interim. Subsequent evaluations as clinically indicated.		X								
Amsler grid Test	To be performed by treating physician or nurse (or other appropriate study personnel).		X			X		X		X	
Ophthalmologic Exam	To be performed by an ophthalmologist. See Section 9.6.7 for exact assessments.		X	As clinically indicated (eg, based on abnormal Amsler grid test, see Attachment 5)							
Documentation of hearing loss (Grade 2 or higher) ¹	Hearing loss (where applicable) will be documented in the source for cisplatin-ineligible population and performed as		X								

Assessments/ Procedure	Notes	Molecular Eligibility Screening Period	Full-Study Screening Period	Treatment Cycle 1 ^g		Treatment Cycle 2 ^{g, 3}		All Other Cycles ^g		End-of-Treatment ^{a, g}	Follow-up Period ^{a, g}
		≥28 days prior to C1D1	Within 28 days prior to C1D1	Day 1	Day 15 (±2)	Day 1 (±2)	Day 15 (±2)	Day 1 (±2)	Day 15 (±2) ^f	Within 30 Days (+7) of last dose	Every 12 weeks
	clinically indicated. See Section 9.6.11.										
Laboratory Assessments (by the local laboratory)											
Hematology	See Section 9.6.2; May be obtained up to 2 days prior to each cetrelimab dose.			X	X	X	X	X	X	X	
Chemistry ^h	May be obtained up to 2 days prior to each cetrelimab dose; for exact assessments, see Section 9.6.2.			X	X	X	X	X	X	X	
PO ₄	May be obtained up to 2 days prior to each cetrelimab dose; for exact assessments, see Section 9.6.2.			X	X	X	X	X			X
PTH	May be obtained up to 2 days prior to each cetrelimab dose; for exact assessments, see Section 9.6.2. After C6D1, PTH to be done every 3 rd cycle. Results not required before dosing.			X		X	X		X		X
TSH, T3, FT4	May be obtained up to 2 days prior to		X	Day 1 of every other cycle starting at C2D1							

Assessments/ Procedure	Notes	Molecular Eligibility Screening Period	Full-Study Screening Period	Treatment Cycle 1 ^g		Treatment Cycle 2 ^{g, 3}		All Other Cycles ^g		End-of-Treatment ^{a, g}	Follow-up Period ^{a, g}
		≥28 days prior to C1D1	Within 28 days prior to C1D1	Day 1	Day 15 (±2)	Day 1 (±2)	Day 15 (±2)	Day 1 (±2)	Day 15 (±2) ^f	Within 30 Days (+7) of last dose	Every 12 weeks
	each cetrelimab dose; for exact assessments, see Section 9.6.2.T3 at Screening then only as clinically indicated.										
Serology	See Section 9.6.2. Results obtained within 60 days of C1D1 are acceptable.		X								
Pregnancy test (pre-dose)	For women of childbearing potential, serum at Screening (β-hCG) - obtain ≤7 days of C1D1. Serum or urine thereafter. See Section 9.6.4.		X			X		X		X	X ^d
Efficacy Assessments											
Disease assessment and response evaluation	Radiologic assessment by CT (preferred) or MRI of all disease sites (present and suspected) documented at Screening. The same methodology should be used throughout the study. Refer to		X						Every 6 weeks until Week 48 (±3 days), then every 12 to 24 weeks (±14 days) until disease progression. The timing of disease assessments should be calculated from C1D1 and the schedule should be maintained regardless of cycle delays and/or study drug interruptions. For subjects who discontinue study drug before disease progression, tumor assessments should continue as scheduled (see Section 9.1.3). Tumor response will be evaluated according to RECIST 1.1 criteria (Seymour 2017). All unconfirmed PR/CR require confirmation of response as per RECIST 1.1.		

Assessments/ Procedure	Notes	Molecular Eligibility Screening Period	Full-Study Screening Period	Treatment Cycle 1 ^g		Treatment Cycle 2 ^{g, 3}		All Other Cycles ^g		End-of-Treatment ^{a, g}	Follow-up Period ^{a, g}
		≥28 days prior to C1D1	Within 28 days prior to C1D1	Day 1	Day 15 (±2)	Day 1 (±2)	Day 15 (±2)	Day 1 (±2)	Day 15 (±2) ^f	Within 30 Days (+7) of last dose	Every 12 weeks
	Section 9.2. for details. Disease assessments done within 35 days prior to C1D1 may be used as the Screening disease assessment.										
Ongoing Review											
Adverse Events	X - Continuous from signing of Full-Study ICF to up to 100 days after the last dose of study treatment or until the start of subsequent anticancer therapy. An AE should be monitored until it resolves to baseline, stabilizes, or is deemed irreversible, subject dies, or subsequent therapy is started, whichever occurs first.										
Concomitant medications	X - Continuous from signing of Full-Study ICF to up to 100 days after the last dose of study treatment or until the start of subsequent anticancer therapy, if earlier. See Section 8.										
Posttreatment Assessments											
Survival evaluation	Contact subject every 12 weeks (±7 days) after the last dose of study treatment by office visit, phone call or e-mail. See Section 9.1.4.										X
Subsequent anticancer therapy	Contact subject every 12 weeks (±7 days) after the last dose of study treatment by office visit, phone call or e-mail. See Section 9.1.4.										X

Abbreviations: AE = adverse event; aPTT = activated partial thromboplastin time; b-hCG= beta-human chorionic gonadotropin; C = cycle; CR= complete response; CT = computed tomography; ctDNA=circulating tumor DNA; D = day; ECG = electrocardiogram; ECOG = Eastern Cooperative Oncology Group; EOI=end of infusion; FGFR= fibroblast growth factor receptor; FT4= free thyroxine; ICF = informed consent form; INR = international normalized ration; MRI = magnetic resonance imaging; MUGA= multi-gated acquisition scan; OCT = optical coherence tomography; PBMC=peripheral blood mononuclear cell; PD-L1 = programmed cell death ligand 1; PE = physical examination; PK = pharmacokinetics; PO4 = phosphate; PR= partial response; PS = performance status; PT = prothrombin time; PTH=parathyroid hormone; RECIST = Response Evaluation Criteria in Solid Tumors; RP2D=recommended Phase 2 dose; T3= triiodothyronine; TCR=T cell antigen receptor; TSH= thyroid stimulating hormone

^aThe End-of-Treatment Visit will occur within 30 days after the subject discontinues treatment for any reason. This assessment should be done prior to the subject starting a new therapy. Follow-up visits will occur every 12 weeks (±7 days).

^bFor subjects signing a Full-Study ICF for the purpose of undergoing a new tissue biopsy for molecular screening, the 35-day window starts with the first planned study-related procedure other than the tissue biopsy; however, AEs will need to be collected from the time of Full-Study ICF sign off.

^c Schedule for Phase 2 will be determined once RP2D from the Phase 1b erdafitinib + cetrelimab cohort has been identified.

Assessments/ Procedure	Notes	Molecular Eligibility Screening Period	Full-Study Screening Period	Treatment Cycle 1 ^g		Treatment Cycle 2 ^{g, 3}		All Other Cycles ^g		End-of-Treatment ^{a, g}	Follow-up Period ^{a, g}
		≥28 days prior to C1D1	Within 28 days prior to C1D1	Day 1	Day 15 (±2)	Day 1 (±2)	Day 15 (±2)	Day 1 (±2)	Day 15 (±2) ^f	Within 30 Days (+7) of last dose	Every 12 weeks

^d Physical examination, vital signs, and pregnancy testing at first follow-up visit (12 weeks after last dose).

^e C1D1 must occur no more than 3 days after the Randomization transaction in IWRS.

^f Subjects on erdafitinib monotherapy (including subjects assigned to Arm A, as well as any subjects who permanently discontinue cetrelimab) do not need to complete the Day 15 visit after Cycle 3. After Cycle 4, subjects continuing on cetrelimab will switch to Q4W dosing and therefore do not need to complete the Day 15 visit procedures.

^g Guidance for study conduct for ongoing subjects in the event of a national disaster is provided in [Attachment 10](#).

^h CrCl is calculated by the Cockcroft-Gault formula ([Attachment 8](#)).

ⁱ Consent for molecular screening (but not full-study screening) may be performed remotely including consent by telephone or video consultation, unless not permitted according to local guidance.

^j Pre-dose only for Arm A.

^k Post-dose ECGs for subjects receiving erdafitinib monotherapy should be recorded 2 to 4 hours after the erdafitinib dose on C2D1 and, if possible, 2 to 4 hours after the erdafitinib dose on C4D1. Post-dose ECGs for subjects receiving erdafitinib and cetrelimab in combination should be recorded as soon as possible upon completion of infusion on C2D1 and C4D1. The End-of-Treatment ECG may be performed at any time during the End-of-Treatment Visit. Additional ECGs may be performed during the study as clinically indicated.

^l Audiometry tests that were performed prior to consent for the full-study was obtained is permitted to be collected as long as it is documented this procedure was performed as part of standard of care and not specifically for study purposes.

Appendix 3 Table 2: Pharmacokinetic, Immunogenicity, and Biomarker Samples for the Phase 2 Erdafitinib +/- Cetrelimab Cohort (Up to and Including Amendment 4)

Assessments/ Procedure	Notes	Molecular Eligibility Screening Period	Full- Study Screening Period	Treatment Cycle 1		Treatment Cycle 2, 3		All Other Cycles		End of Treatment ^a	Follow- up Period ^a
		≥28 days prior to C1D1	Within 28 days prior to C1D1	Day 1	Day 15 (±2)	Day 1 (±2)	Day 15 (±2)	Day 1 (±2)	Day 15 (±2)	Within 30 Days (+7) of last dose	Every 12 weeks
Note: These samples should be drawn on the day study drug is administered. ^b											
Erdafitinib PK ^c (Both Arms)	Pre-dose erdafitinib ^d unless otherwise specified. See Section 9.3.			X	X	Pre-dose erdafitinib C2 & C3; 4h post erdafitinib C2D1 only ^e		Pre-dose erdafitinib C5; 4h post erdafitinib C5D1 only ^e			
Erdafitinib Protein Binding Blood Sample (Both Arms)	4 hrs Post-dose See Section 9.3.					C2D1					
Cetrelimab PK ^c (Arm B only)	Pre-infusion ^d and EOI ^f unless otherwise specified. See Section 9.3.			X	X	X		C4 & C5		Any time during visit	At first follow- up visit, if possible
Cetrelimab Immunogenicity (Arm B only)	Pre-infusion ^d See Section 9.3.			X	X	X		C4 and every other cycle starting at C5D1		Any time during visit	At first follow- up visit, if possible
CCI [REDACTED]	A tumor biopsy can be taken at any time during a visit if a subject shows PD		X			C2D1 (±3 days)				PD	

Assessments/ Procedure	Notes	Molecular Eligibility Screening Period	Full- Study Screening Period	Treatment Cycle 1		Treatment Cycle 2, 3		All Other Cycles		End of Treatment ^a	Follow- up Period ^a
		≥28 days prior to C1D1	Within 28 days prior to C1D1	Day 1	Day 15 (±2)	Day 1 (±2)	Day 15 (±2)	Day 1 (±2)	Day 15 (±2)	Within 30 Days (+7) of last dose	Every 12 weeks
	anytime throughout the study ^h										
CCI [REDACTED]	Pre-dose erdafitinib ^d			X	X	X	X				
CCI [REDACTED]	Pre-dose erdafitinib ^d			X	X	X	X			Any time during visit	
CCI [REDACTED]	Pre-dose erdafitinib ^d unless otherwise specified.			X		C3D1		C5D1		Any time during visit	
CCI [REDACTED]	Archival or fresh biopsy tissue must be available for biomarker analysis.	X									

Abbreviations: ctDNA= circulating tumor DNA; EOI=end of infusion; FGFR= fibroblast growth factor receptor; PD= progressive disease; PD-L1 = programmed cell death ligand 1; PK = pharmacokinetics; PBMC = peripheral blood mononuclear cells; TCR = T cell antigen receptor

^a The End-of-Treatment Visit will occur within 30 days after the subject discontinues treatment for any reason. This assessment should be done prior to the subject starting a new therapy. Follow-up visits will occur every 12 weeks (±7 days).

^b The sampling schedule may be adjusted based on PK analysis output generated during the study or other safety concerns.

^c If dose delay occurs, then samples should be collected on the actual day of drug administration, not on the originally scheduled administration day.

^d On the day in which both drugs are given, erdafitinib oral dose will be administered prior to cetrelimab IV infusion. Pre-dose PK sample for erdafitinib and Pre-infusion PK and immunogenicity samples for cetrelimab may be collected up to 30 minutes before dosing, respectively.

^e Timepoint is relative to the dosing of erdafitinib. Erdafitinib PK samples may be collected during the cetrelimab infusion if necessary; however, the sample should be drawn from the contralateral arm (opposite the cetrelimab infusion site).

^f As soon as possible after EOI.

^g Paired biopsies at Screening and C2D1 are optional. The biopsy upon PD is also optional for all subjects. High-risk areas of metastases such as brain, pancreas, and lung should not be considered as an accessible site for biopsy. Biopsies will be collected to aim to have a minimum of 15 evaluable biopsy pairs.

^h Tumor biopsy to be taken within 2 weeks of documented disease progression. Note: Additional samples may be collected at any time for assessment of AEs as clinically appropriate.

